This protocol is a 12-site multicenter RCT (N=492), with Seattle as the prime site, partnering with transplant centers in Ohio, Minnesota, Wisconsin, Michigan, Massachusetts, Pennsylvania, New York, Florida, Kansas, Illinois, and Texas. This provides age, region and rural/urban diversity. Participants randomized to the intervention will receive immediate access to the tailored online program, with options for social-media, adding stepped care self-management calls for those not improving by a 6-week interim assessment for those in group 1. Control participants will receive access to a website that provides annotated links to publicly available HCT and cancer websites as well as delayed internet site access. Outcomes will be assessed at 6 weeks, 3 months and 12 months.

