
#### Stratification and Randomization

Those who complete the baseline assessment but are determined to be ineligible after baseline assessment will be given access to the online INSPIRE site as a courtesy. Those who meet all eligibility criteria will be randomized based on the stratification criteria described below. If any one of the following scores on baseline patient reported outcomes (PRO) is impaired, the participant will be randomized within 'Group 1,' if no scores are impaired the participant will be randomized within 'Group 0' for the primary and secondary endpoints: a) Cancer and Treatment Distress (CTXD score <0.9 vs.  $\geq 0.9$ ), b) cardiometabolic health care adherence (<80% vs.  $\geq 80\%$ ) and c) cancer health care adherence (<80% vs.  $\geq 80\%$ ). Note that each of these endpoints of the study has a measure cut-point for eligibility for Group 1 randomization required at baseline, and these are the threestratification parameters below. However, all eligible participants will be randomized

as they will all contribute data for secondary analyses. After minimum required baseline assessment is complete and eligibility confirmed, the Project Manager will fax the registration office with stratification data for randomization. Stratification factors are based on whether the participant exceeded or fell below the cut-offs for these endpoints, as determined by baseline screening values, prior to randomization. We will not stratify on age, sex, cGVHD treatment, or race/ethnicity because we believe these will be balanced adequately between study arms through random selection, and we will adjust, or stratify on these factors as needed in analyses. Participants in both groups will then be randomly assigned to either the "Control" or "Intervention" arms. The PIs and Biostatistician will review participation rates within each stratum annually and adjust the algorithm if needed. Once enrollment is complete, the sampling probability relevant to each participant will be stored in the database for use in analyses. Randomization assignment of the participant will be communicated to the participant through email. A diagram of study randomization is shown in Figure 2 and will occur as follows.

[figure not shown]
Group 1. Meets all eligibility and has one or more elevated distress or low cardiometabolic or cancer health care adherence and is randomized to one of the two groups, intervention or control.

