*Stepped Care Self-Management Telehealth Contacts.* Group 1 intervention participants who at the T2 (6 weeks) indicate no use of the online program, or lack knowledge of their cardiometabolic or subsequent malignancy risks, or do not indicate improvement in distress, will receive telehealth contacts. These will be three to four calls via phone. Calls will last 20-30 minutes for the first call and 10-20 minutes for the 'booster' calls. They will be led by a 'coach' trained by the clinical investigators in HCT and self-management skills, using a manual to deliver call content focused on assisting survivors with using the self-management skills in the online program. This is a brief, manualized intervention is designed to be sustainable without extensive clinical training and has been tested. The first session will focus on impairments indicated by the T2 6-week screening PRO. The coach and participant will make shared decisions, led by the participant, on goals and an action plan for addressing deficits, and elicit potential barriers and their solutions based on chronic disease self-management models (Figure 1).[1, 84, 133, 140-143] The second and third 'booster' calls will review progress on the action plan, address barriers and agree on a revised plan if needed. Participants and coaches will decide whether a fourth call would be helpful based on the complexity and difficulty of the goals and action plans. The contacts will be audiotaped for process evaluation

of content and fidelity to the self-management script.

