## Measurement Time Points

The measures and their administration time points for three of the four assessments are listed in Table 1: baseline, 3 and 12 months. For group 1 intervention participants only, there will also be a brief orientation call for the study at 2 weeks, and an assessment at 6 weeks, that determines distress and knowledge of survivor health risks. Distress is measured on a 0-10 distress thermometer rating scale (0=no distress, 10=extreme distress) is >5, along with the first 2 items on the PHQ scored <=2 indicating low distress and depression symptoms. The distress thermometer is a widely used, validated and reliable measure of distress in cancer survivors.[144-147] Knowledge of HCT Survivor Health Risks is an 11-item screening for cardiometabolic and subsequent malignancy risks. Items are scored 0 ('my risk is higher') or 1 ('my risk is not different' or 'not sure') with a score >2 indicating inadequate knowledge of risks and eligibility for telehealth stepped care. The third criterion is whether the participant has viewed at least 3 pages of the online INSPIRE site. If any one of these 3 progress criteria are not met, intervention participants are stepped into telehealth self-management contact as described in Treatment section 7.5.1.

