This is a descriptive aim defining costs and resource requirements. Data relevant to resource utilization (costs) and methods of collection are described in section 8.3 Cost and Resource Tracking. All costs associated with the intervention and, separately, the control arms of the study for the Group 0 and Group 1 subjects in the study will be summed and standardized to per person costs. We will use these amounts to calculate an incremental cost ratio for the online intervention program and telehealth intervention component compared to the control cost, similar to the method described by Mandelblatt et al.[171, 172] The costs of maintaining the various components of the program, relative to their use, will be calculated separately for those in the Group 0 and 1 intervention arms, specific to maintaining the social media site, the internet program, and the telehealth calls (Group 1 only) relative to the number of participants using those components among intervention participants.

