### Secondary Analyses

Secondary endpoints will include depression, process measures describing internet study reach and utilization, as well as outcomes of knowledge of survivorship needs. We will compare secondary outcomes knowledge of health care needs between study arms using similar analytic methods as for the primary outcomes (both binary and continuous outcomes). We will also carry out subset analyses within stratum defined by the degree of utilization of the resources (i.e. more than one page viewed of internet site – see below for alternate definitions), and receipt of the phone calls if designated, to evaluate whether, among “users”, the tailored intervention has stronger effects.

Further analyses will identify risk factors for disparities in survivorship HCA in HCT survivors. Study reach, adoption and attrition process measures will be reported descriptively.

Primary analyses will be based on 12 month outcome measurements, but we will utilize the 3 month time point in secondary longitudinal analyses modeled after those carried out in DuHamel et al.[30] Additional secondary analyses will include evaluation of the impact of the internet intervention on continuous versions of the primary endpoints, but among all participants randomized, including those not meeting criteria for inclusion in primary analyses. This will provide estimates of the impact of study intervention on an unscreened population which would be a likely dissemination methodology.

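### The all-randomized analysis estimates a program steered by baseline scores; it does not estimate delivery without a baseline screen

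*Combined protocol and SAP*

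**What the plan says.** Section 12.8 adds a secondary analysis of the continuous primary endpoints "among all participants randomized, including those not meeting criteria for inclusion in primary analyses", and draws from it the conclusion "This will provide estimates of the impact of study intervention on an unscreened population which would be a likely dissemination methodology". The sentence that sets up the analysis names the internet intervention; the concluding sentence names the study intervention.

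Other sections fix what each participant can receive:

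- **Section 7.5, Stratification and Randomization:** "If any one of the following scores on baseline patient reported outcomes (PRO) is impaired, the participant will be randomized within" Group 1. The scores are CTXD (0.9 or above), HCA-cardio (below 80%) and HCA-cancer (below 80%). Participants with none impaired form Group 0. Section 12.2 (Design) randomizes the two groups separately.
- **Section 8, Measurement Time Points:** the limit is worded "group 1 intervention participants only, there will also be a brief orientation call for the study at 2 weeks, and an assessment at 6 weeks".
- **Section 7.6, Stepped Care:** the telehealth calls go to "Group 1 intervention participants who at the T2 (6 weeks) indicate no use of the online program", or who fail the knowledge or distress criterion.
- **Section 1.0:** the overview describes "adding stepped care self-management calls for those not improving by a 6-week interim assessment for those in group 1".
- **Section 12.7, Aim 3 plan:** component costs include "the telehealth calls (Group 1 only").

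Two places do not carry this limit. The consent description (Section 7.3) offers both kinds of call, as optional, to the intervention arm as a whole. The analysis plan for Hypothesis 2 (Section 12.7) defines the need for stepped care in the intervention arms of both groups.

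**The concern.** Every randomized participant has been scored at baseline, and the scores determine the package. Intervention participants in Group 1 can receive the online program plus the orientation call, the 6-week check and, if triggered, the calls. Those in Group 0 receive the online program and mailings without these contacts. Section 7.6 also points participants to landing pages according to their elevated baseline scores, so part of the online tailoring uses the screen too.

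The concluding sentence of Section 12.8 speaks of a dissemination method, and so of how the program would be delivered as well as who would be analysed. Implementation through the registry is a stated goal (Section 1.0, Aim 3). If the pooled estimate were quoted as the effect of a program delivered without screening, it would be credited to a form of delivery the trial did not run. It would also not match the Aim 3 costs, which treat telehealth as a Group 1 component.

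**Working it through.** **1. The plan's own figures.** The disputed sentence states no number. The nearest are the detectable effects for the continuous endpoints in Section 12.7: 0.52 SD with 71 per arm (CTXD) and 0.47 SD with 86 per arm (HCA-cardio), at 80% power and two-sided alpha 0.025. With detectable effect = (2.2414 + 0.8416) × √(2/n):

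- n = 71: 3.0830 × 0.1678 = 0.517
- n = 86: 3.0830 × 0.1525 = 0.470

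Both reproduce. They belong to the 197 and 239 participants impaired on each endpoint, and they do not bear on the present point.

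**2. What each group is offered** (reading the sections that carry the Group 1 limit):

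| | Intervention | Control |
|---|---|---|
| Group 1 | Online program, mailings, 2-week call, 6-week assessment, telehealth if triggered | Links website, mailed care plan, delayed access |
| Group 0 | Online program, mailings | Links website, mailed care plan, delayed access |

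**3. What the pooled contrast estimates.** Let π be the Group 1 share, o₁ and o₀ the effects of the online package in the two groups, and s₁ and s₀ the average effects that the extra contacts add, or would add, in each. Assume similar retention in both groups.

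- As run: π(o₁ + s₁) + (1 − π)o₀
- Online package for everyone, no contacts: πo₁ + (1 − π)o₀. The pooled value differs from this by πs₁.
- Contacts open to everyone: π(o₁ + s₁) + (1 − π)(o₀ + s₀). The pooled value differs from this by (1 − π)s₀.

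Group 1 has no online-only arm, so s₁ is not identified. No one in Group 0 receives the contacts, so s₀ is not identified. The second question is a real one, because two of the three 6-week criteria (knowledge of risks, pages viewed) are not baseline-impairment criteria.

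**4. Size of the groups.**

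- Section 12.2 expects about 305 of 492 in Group 1: 305/492 = 62.0%. Group 0 is 492 − 305 = 187, or 38.0%.
- The 305 is described by the two primary outcomes, whereas Section 7.5 also admits participants to Group 1 on HCA-cancer alone. Section 8 (Secondary Outcomes) gives 45% non-adherent. If that rate holds independently among the 187, then 187 × 0.45 = 84 move to Group 1, giving 389/492 = 79.1%. Group 0 becomes 187 × 0.55 = 103, or 20.9%.

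Group 0 is therefore about 21% to 38% of those randomized. With equal allocation, that is about 103/2 = 51 to 187/2 = 94 intervention participants. The pooled value contains 62% to 79% of s₁ and none of s₀.

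**5. Precision of a Group 0 estimate.** Assume the plan's 72% retention, 80% power and two-sided alpha 0.05 (the plan sets none for this analysis). Detectable effect = (1.960 + 0.842) × √(2/n):

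- Group 0 of 187: n = 187 × 0.72/2 = 67 per arm, 0.48 SD
- Group 0 of 103: n = 103 × 0.72/2 = 37 per arm, 0.65 SD
- All randomized: n = 492 × 0.72/2 = 177 per arm, 0.30 SD

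**The case against.** The strongest reply is that the adjective in Section 12.8 describes the population, and that the preceding sentence defines that population as everyone randomized, impaired or not. On that reading the claim is about who is analysed. Both groups are randomized, routing by score is part of the program, and the intention-to-treat effect of a stepped program is properly an average over routed intensities. This stands. A reader might infer that the design cannot say anything about survivors not selected for impairment; the documents do not support that, because the pooled contrast is a valid randomized estimate in such participants.

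It is also fair that no section says a disseminated program would drop the baseline assessment. Section 1.0 plans to build on the registry's assessment infrastructure, which may point the other way. But if the screen is kept, the sentence should say so; if it is dropped, the trial has no arm that matches. The wording needs qualifying in either case.

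Two further inferences should be resisted:

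- Multiplying 0.52 or 0.47 by the Group 1 share to obtain a diluted effect. Those values apply to endpoint-specific subsets, and the 305 may not be all of Group 1. A smaller effect in unimpaired participants could also arise with identical contacts.
- Reading an arm-by-group interaction as the effect of the telehealth step. Group is defined by baseline impairment, so impairment and contact intensity cannot be separated.

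Finally, this is a secondary analysis with no allocated alpha or decision rule, and no primary result depends on it.

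**Conclusion.** The point holds as one of interpretation. The all-randomized comparison validly estimates, in survivors not selected for impairment, the effect of a program in which baseline scores decide who can receive the orientation call, the 6-week assessment and the telehealth step. It does not estimate delivery without that screen, so the dissemination statement goes further than the design.

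About 21% to 38% of those randomized fall outside the contacts. The upper figure takes 305 as all of Group 1; the lower adds HCA-cancer non-adherence at 45% under independence. The resulting difference in SD units cannot be derived from the documents, because the effect of the contacts is not identified in either group.

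The conclusion rests on the sections that limit the contacts to Group 1. The consent description and the Hypothesis 2 plan do not carry that limit, and the passages must be reconciled.

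**What to change.** 1. In Section 12.8, describe the estimate as: *the effect, in participants not selected for impairment, of a program in which baseline scores direct who is offered the orientation call, 6-week assessment and telehealth step*. Remove or qualify the statement about dissemination to an unscreened population, and use one term for the intervention throughout the paragraph.
2. Beside the pooled value, report the arm effect separately in Group 0 and Group 1, with an arm-by-group term. Both are randomized comparisons. State that contact intensity and baseline impairment are confounded, so the interaction does not isolate the effect of the step.
3. Reconcile the consent description (Section 7.3) and the Hypothesis 2 analysis set (Section 12.7) with Sections 1.0, 7.6, 8 (Measurement Time Points) and the Aim 3 plan on whether Group 0 can receive these contacts.

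The cost is a few lines of text and extra rows in a secondary table, with no new data or participants. The downsides are an imprecise Group 0 estimate (detectable effect about 0.48 to 0.65 SD under the assumptions above) and a narrower claim about dissemination.

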### 12.9 Process Descriptive Analyses

Evaluation of the telehealth self-management calls will be based on 1) fidelity scored from audiotape reviews, 2) coach ratings, 3) completion rates of scheduled calls and 4) completion of action plans, and 5) barriers identified during calls. Additional descriptive analyses will be conducted on the process elements defined in section 8.4 Process Measures.

## **13.0 TERMINATION OF STUDY**

Survivors in the intervention group will complete the intervention approximately 12 months after beginning (i.e., the date the patient received notification of randomization and website access). After completing the 12-month assessment, they will receive notification that they have completed participation in the study. Survivors will continue to have full access to the website after their official study participation has ended until the end of the study.

Survivors in the control (delayed internet site access) group will have full internet program access from the time they complete the 12-month assessment until the end of the study.

Survivors may withdraw from the study whenever they request to do so.

